7.1 Study design

The proposed study is an open-label, exploratory, randomized control trial examining the effect of FSH and rLH (Luveris) versus FSH alone on the number of mature oocytes available for cryopreservation in non-hormone sensitive onco-fertility patients. These patients include those diagnosed with malignancy other than breast, uterine and ovarian cancer.

Given that the care of oncology patients is time sensitive, a random start of the treatment cycle is the usual approach in our clinic, with no prior priming. The patient has a random serum levels of estrogen, progesterone, LH, FSH and HCG levels obtained. A transvaginal ultrasound is performed

as well, and the stage of the cycle is determined. Based on the stage of the cycle, gonadotropin starting time is planned accordingly and the starting dose will be individualized based on AFC as detailed below.

- Early follicular phase: Gonadotropin stimulation started. A GnRH antagonist will be given once the dominant follicle measures >1.4 cm.
- Mid to late follicular phase: patients who have a dominant follicle >1.5 cm with an E2 >300 and a progesterone <5 will be triggered usually with HCG (Ovidrel 250 mcg subcutaneous). After three days gonadotropin stimulation is started.
- Start of luteal phase: start gonadotropin stimulation and once the dominant follicle measure >1.4, a GnRH antagonist will be given.

Patients will be randomly assigned in a 1:1 ratio to either treatment or control group. Treatments in each of the trial arms will be as follows:

- a) Treatment arm: Patients will self-administer a subcutaneous injection of Gonal-F (FSH) in addition to Luveris daily until a pre-set criteria to trigger ovulation is reached.
- b) Control arm: Patients will self-administer a subcutaneous injection of Gonal-F (FSH) alone daily until a pre-set criteria to trigger ovulation is reached.

Transvaginal ultrasound and bloodwork monitoring is initiated to monitor the ovarian response. Once the patient meets one of the following two criteria

- a) A serum estradiol (E2) of greater than 2,000 pmol/L
- b) A follicle measuring greater than 14 mm,

A daily, subcutaneous injection of a GnRH antagonist (Cetrotide or Ganirelix 0.25 mg) will be administered by the patient subcutaneously to prevent an endogenous surge in LH. Monitoring of the ovarian response will continue until there are 3 or more follicles visualized by transvaginal ultrasound with a mean diameter of ≥17 mm. Ovulation will be subsequently triggered with a subcutaneous injection of HCG or GnRH agonist depending on the managing IVF physician. If a GnRH agonist trigger is chosen, twelve hours after their trigger medication, patients will return to the clinic for blood work including LH and progesterone as per standard procedure. This is a routine confirmatory blood test to confirm that an endogenous LH surge has occurred. In approximately less than 5% of cases, the GnRH agonist trigger fails to elicit an optimal surge, which may require a "rescue" low-dose hCG trigger to be administered 24 hours following the initial trigger. The decision to administer a "rescue" trigger will be at the discretion of the managing IVF physician. Transvaginal, ultrasound-guided oocyte retrieval will be performed approximately 36 hours following the administration of the initial trigger.

Once the oocytes are retrieved, if the patient desires to cryopreserve oocytes, mature oocytes will be cryopreserved by vitrification process. If embryo cryopreservation is planned, the retrieved oocytes will be fertilized in the lab using traditional IVF or ICSI. Embryos will be grown to day 5 and all "good quality" blastocysts will be cryopreserved using vitrification. At our clinic, day 5/6 embryos are considered "good quality" for cryopreservation if they are at least a grade 2BB (or above) on day 5 and/or a 3CC (or above) on day 6, according to the classification system by Gardner and Schoolcraft, 1999 [25].

7.2 Inclusion criteria

Patients will be included in the study based on the following criteria:

- Between the ages of 18 and 40.
- Undergoing IVF for fertility preservation (freezing all oocytes or embryos)
- Diagnosed with a non-hormone sensitive malignancy (malignancy other than breast, uterine and ovarian cancer)
- GnRH antagonist protocol (standard of care for all fertility preservation patients)

7.3 Exclusion criteria

Patients will be excluded from the study based on the following criteria:

- Any contraindication to treatment with gonadotropins (including medical history or risk factors for TE, hypersensitivity to gonadotropins or to any of the excipients).
- Congenital hypogonadotropic hypogonadism unrelated to the oncological condition.
- Previous adverse or allergic reaction to luteinizing hormone or any of its drug components.
- Had prior radiotherapy to the abdomen or pelvis
- Prior chemotherapy
- Prior history of deep vein thrombosis, or pulmonary embolism
- Patients with a diagnosis of hormone sensitive cancer including ovarian, uterine, or mammary carcinoma
- Patients with uncontrolled thyroid or adrenal failure
- Patients with active, untreated tumors of the hypothalamus and pituitary gland
- Patients who are lactating
- Patients with a known diagnosis of primary ovarian failure
- Previous participant of this study

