Physiologically, FSH is the main trophic hormone that stimulates ovarian follicle development [6]. However, LH also has several roles in follicular development and is present at low levels throughout the early follicular phase of the menstrual cycle during the time of follicular recruitment. According to the two-cell two-gonadotropin theory, LH is responsible for stimulating the ovarian thecal cells to produce androgens. Under the influence of FSH, granulosa cells use these androgens to produce estrogens, which are critical for healthy follicular development [7]. LH is also involved in ovulation induction, completion of meiosis I, and follicular luteinization and progesterone production.

In 2005, Health Canada approved the use of lutropin alfa, a recombinant human luteinizing hormone, for treatment of hypogonadotropic hypogonadism. There is growing evidence that in addition to patients with hypogonadotropic hypogonadism, patients undergoing IVF with a history of low ovarian reserve, poor ovarian response, or advanced maternal age (>35 years) may also benefit from the addition of rLH. A systematic review and meta-analysis of 40 randomized trials totaling 6443 patients undergoing IVF/ICSI using FSH and rLH versus FSH alone suggested that adding rLH to FSH resulted in a 9% increase in clinical pregnancy rates, with a 30% increase in poor responders [8]. Another meta-analysis supported the addition of rLH for patients >35 years, quoting higher pregnancy rate [9].

There has been increased interest in the fertility community of using rLH in oncology patients. In this population, the hypothalamic gonadal axis may be affected given the possible association between malignancy and a catabolic state, increase in stress hormone, and malnutrition [10,11].

Accordingly, some have suggested there may be an impact on ovarian reserve, oocyte quality, and the need for a higher dose of gonadotropins [12,13]. Currently, GnRH antagonist protocol is used as standard of care in this population to avoid delay in their cancer treatment and minimize the risk of ovarian hyperstimulation syndrome [14,15].

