Fertility preservation is performed before the initiation of cancer therapy in an effort to reduce its cytotoxic effects on ovarian function. However, recent literature has demonstrated that ovarian function is reduced in cancer patients even before starting cancer treatment. A case series reported a greater proportion of immature oocytes per cycle and lower maximal levels of estradiol in various cancer patients compared to patients with isolated tubal infertility, suggesting the negative impact

of cancer on oocyte maturation [12]. A matched cohort study reported lower AMH levels in patients with lymphoma before chemotherapy, warranting higher doses of gonadotropins for ovarian stimulation to maximize the number of oocytes retrieved before chemotherapy [13].

Studies have highlighted that administration of exogenous FSH and LH is essential for patients with hypogonadotropic hypogonadism [23], which is consistent with the current approved use of rLH by Health Canada. Evidence also supports the use of rLH in poor responders with advanced maternal age [9]. There is growing concern in the literature that some oncology patients may be poor responders prior to cancer therapy due to hypothalamic gonadal axis dysfunction secondary to their malignancy [2]. With evidence suggesting that the hypothalamic gonadal axis is affected in the oncology population, and that rLH may improve fertility preservation outcomes in a subgroup of patients that mimic hypogonadotropic cases, the efficacy of rLH in oncology patients is plausible.

Given the mixed literature of rLH efficacy in the oncology population and the improved fertility preservation outcomes in various patients supplementing ovarian stimulation with rLH, an exploratory randomized controlled trial is warranted to definitively address the safety and efficacy of rLH in non-hormone sensitive cancer patients.

6. Significance of the study

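### Section 7.3 excludes only congenital hypogonadotropic hypogonadism, so women with a known acquired form unrelated to their cancer can be randomised to FSH alone, although section 5 calls LH essential in that condition

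*Protocol*

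**What the plan says.** Protocol section 7.3 (Exclusion criteria) has one criterion that names hypogonadotropic hypogonadism (HH): "Congenital hypogonadotropic hypogonadism unrelated to the oncological condition". A second criterion in the same list touches a possible cause of acquired HH: "Patients with active, untreated tumors of the hypothalamus and pituitary gland". Prior radiotherapy is an exclusion only when given to the abdomen or pelvis.

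The background section states that "Health Canada approved the use of lutropin alfa, a recombinant human luteinizing hormone, for treatment of hypogonadotropic hypogonadism". Section 5 (Rationale) adds: "Studies have highlighted that administration of exogenous FSH and LH is essential for patients with hypogonadotropic hypogonadism". Neither statement separates congenital from acquired disease.

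Section 5 then sets out the mechanism under test, the concern that "some oncology patients may be poor responders prior to cancer therapy due to hypothalamic gonadal axis dysfunction secondary to their malignancy". It argues that rLH may help a subgroup resembling HH.

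Section 7.1 gives the allocation: "Patients will be randomly assigned in a 1:1 ratio to either treatment or control group". The control arm receives FSH alone.

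**The concern.** The protocol treats the value of LH in HH as settled and asks whether it also helps cancer patients whose axis may be disturbed by their disease. An exclusion for HH of other origin fits that plan. As worded, it removes only the congenital form. A woman with an established acquired form unrelated to her cancer enters the trial, and if allocated to control she does not receive what section 5 calls essential, in a time-sensitive cycle before gonadotoxic treatment.

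Two things are at stake. For such a patient, the protocol's own text leaves no equipoise. For the trial, the population becomes a mixture: mostly women for whom the question is open, plus possibly a few for whom the document treats it as answered. That makes the result slightly harder to read as evidence about cancer patients without pre-existing HH.

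**Working it through.** **1. What the criterion removes.** It sets two conditions that must both hold: congenital, and unrelated to the cancer.

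| Form of HH | As written | With *Congenital* deleted |
|---|---|---|
| Congenital, unrelated to the cancer | excluded | excluded |
| Congenital, related to the cancer | cannot occur | cannot occur |
| Acquired, unrelated to the cancer | **eligible** | excluded |
| Acquired, related to the cancer | eligible | eligible |

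A congenital condition cannot be a consequence of a later cancer, so the second condition is redundant as the sentence stands. It does work only once the first is removed. This suggests, without proving it, that the intended line was between cancer-related and other HH.

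**2. Whether another criterion closes the gap.** Going through sections 7.2 and 7.3:
- The tumour criterion covers active, untreated hypothalamic or pituitary tumours. HH that remains after a treated one is not covered.
- The radiotherapy criterion covers the abdomen and pelvis, not the head.
- The thyroid/adrenal and primary ovarian failure criteria concern other conditions.
- The prior-chemotherapy criterion removes some women with an earlier cancer, but not HH as such.

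None removes a known acquired HH unrelated to the present cancer.

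**3. Whether the rationale covers these women.** It does not. Section 5 concerns dysfunction secondary to the malignancy. HH of another origin falls outside the hypothesis and inside the condition for which section 5 calls LH essential.

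**4. Size.** The plan's own figure first, from section 12.1: SD 4, difference 10 − 8 = 2, n = (16 + 16) × (1.96 + 0.84)² / 2² = 62.72, so 63 per group and 126 in all; 126 / 0.9 = 140 enrolled. This reproduces, and the point does not depend on it. The 2 serves only as a yardstick.

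Let f be the share of such women, d_HH the rLH effect in them and d_0 the effect in everyone else. The overall difference is (1 − f) × d_0 + f × d_HH, so it departs from d_0 by f × (d_HH − d_0). The documents give neither f nor d_HH. Both are assumptions, shown over a range.

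| Assumed f | Women among 140 | Expected on FSH alone | Shift if d_0 = 0 (d_HH = 4; 8) | Shift if d_0 = 2 (d_HH = 4; 8) |
|---|---|---|---|---|
| 1% | 1.4 | 0.7 | 0.04; 0.08 | 0.02; 0.06 |
| 2% | 2.8 | 1.4 | 0.08; 0.16 | 0.04; 0.12 |
| 5% | 7 | 3.5 | 0.20; 0.40 | 0.10; 0.30 |

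Against a difference of 2 oocytes the shift runs from 0.02 / 2 = 1% to 0.40 / 2 = 20%. The upper end needs both the largest assumed share and a benefit of 8 oocytes, which equals the whole control mean of 8 in section 12.1. The table is in raw oocyte counts, whereas section 7.6 adjusts the primary outcome by antral follicle count. The shift on that scale cannot be derived from the document.

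**The case against.** The strongest reply is that the effect on the result is negligible and the control arm is ordinary care. Much of this stands.

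- **Inflation of the rLH effect.** A reader might infer that admitting these women biases the comparison or raises the false-positive rate. The protocol does not support that. With 1:1 randomisation they fall in both arms in expectation, so the estimate is unbiased for the population enrolled. If some enrolled women truly benefit, the overall null hypothesis is false, and a significant result is not a type I error. What remains is effect heterogeneity and its bearing on generalisability.
- **Few patients.** Such a woman would need known HH of another cause, no prior chemotherapy, no active untreated hypothalamic or pituitary tumour, and a new qualifying malignancy. The protocol does not show that even one is expected.
- **Usual care.** The background section says FSH alone is typically chosen for oncology patients at the centre. The document therefore does not show that control patients with HH would receive less than they would outside the trial. But that statement is about oncology patients in general, the same section says the practice is not evidence-based, and it does not address diagnosed HH.
- **Cancer-related dysfunction is in scope on purpose.** Correct. A reader might go further and ask to exclude HH of any cause. That would remove women whose HH is secondary to their malignancy, the mechanism section 5 sets out to test.

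None of this explains why acquired HH unrelated to the cancer should be handled differently from the congenital form.

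**Conclusion.** The eligibility gap is real and rests on the text alone: section 7.3 admits women with known acquired HH unrelated to their cancer, and section 5 and the background section treat the need for LH in HH as established. The two need to be reconciled. It is a matter of equipoise for the individual patient and of a clearly defined target population. It is not a flaw in the randomised comparison.

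The size is unknown. No prevalence and no oocyte yield in HH are given, so the shifts shown are illustrative and no change in the false-positive rate should be claimed. With one or two such women among 140 the effect on the primary result would be minor. The case for acting rests on the patient-level inconsistency and on how little the correction costs.

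**What to change.** Delete *Congenital* from the criterion in section 7.3 and add the word *known*, so that it excludes any known HH unrelated to the oncological condition. Keep the second half of the criterion as it is, so that women whose axis dysfunction comes from their cancer remain eligible. Do not widen it to HH of any cause. If the sponsor does intend to enrol women with acquired HH unrelated to the cancer, section 5 should say so and justify it against its own statement that LH is essential in HH.

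If any such patient has already been randomised, keep her in the intention-to-treat analysis of section 12.2 and report the primary outcome with and without her.

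The cost is a one-line protocol amendment, a slightly narrower population and the loss of at most a few patients. The criterion relies on an existing diagnosis, so no new test is needed. The baseline hormone levels in section 7.5 should not be used to define the exclusion: section 7.1 has them drawn at a random point in the cycle, and the protocol sets no HH threshold for them.

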7.4 Recruitment and informed consent

Patients that are seeking fertility preservation through cryopreservation of oocytes or embryos with a diagnosis of a non-hormone sensitive cancer will be informed about the purpose and aim of the study. If the patient expresses an interest in the study, they will be referred to the clinical research coordinator to discuss the study further and to provide them with additional written information. Patients will be encouraged to ask as many questions as necessary. Communication with the research coordinator may take place in person, over the phone, over Ontario Telemedicine Network, and/or by personal email at the discretion of the patient.

Informed, signed consent may be obtained in-person or via email after communication with the research coordinator. Alternatively, patients may wish to defer consent until a later date. If so, they will be able to contact the research coordinator to sign the consent forms prior to the start of the trial. Patients will be advised that participation in the study is voluntary and they have the right to withdraw from the study, at any point, without penalty or prejudice to the medical care provided.

7.5 Data collection

The following demographic information will be collected from included patients:

Demographics

- Age
- Gravida/para status
- BMI
- Type of malignancy
- Stage of malignancy (if known)
- Prior history of fertility treatment and the specific type
- Baseline FSH, LH, progesterone, estradiol levels
- Ovarian reserve: AMH and AFC (3-8mm) based on the FORT criteria [22].
- Any history of infertility, categorized as:
 - Anovulation including PCOS
 - o Tubal
 - Male Factor Infertility
 - Endometriosis
 - o Unexplained
 - o Other
 - o None
- Total motile sperm count (if freezing embryos)

Characteristics of treatment cycle

- Type of cycle start (follicular vs. luteal phase)
- Total days of gonadotropin stimulation
- Total dose of FSH (IU)
- Total dose of LH (IU)
- Total number of follicles measuring ≥11 mm on the day of trigger
- Total number of follicles measuring 16-22 mm on the day of trigger, according to FORT criteria [22]
- Type of trigger (hCG vs. GnRH-agonist)
- Need for rescue hCG trigger (ie. failed GnRH agonist trigger)
- Bloodwork on day of trigger ± day after trigger:
 - o E2
 - o LH
 - o Progesterone
- Method of fertilization (standard insemination or ICSI or IVF/ICSI split) if freezing embryos
- Use of a dopamine receptor agonist (Cabergoline) to prevent OHSS

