A cohort study by Johnson et al. [16] examined the ovarian stimulation response in oncology fertility preservation patients under various IVF stimulation protocols which included the use of rLH in some patients. The study showed no overall difference in baseline measures of ovarian reserve, total dose of gonadotropin used, or mean number of oocytes retrieved in the group of 50 chemotherapy-naïve cancer patients compared to 50 matched healthy controls. Unfortunately, the number of patients receiving rLH and the total dose received by these patients was not specified. Other studies in the literature examining rLH included case reports and case series, with sample sizes insufficient to generate conclusions regarding rLH efficacy in cancer patients [17-19]. A systematic review concluded that research on ovarian stimulation protocols and outcomes in the onco-fertility literature was inconsistent and of low quality [20], calling for higher quality studies to provide clarity on this topic.

Therefore, we intend to conduct an exploratory randomized controlled trial (RCT) comparing FSH and LH versus FSH alone using a GnRH antagonist protocol in non-hormone sensitive cancer patients undergoing fertility preservation. These patients include those diagnosed with malignancy other than breast, uterine and ovarian cancer.

3. Study Question

In non-hormone sensitive cancer patients undergoing IVF fertility preservation, does the use of FSH and LH for ovarian stimulation lead to a greater proportion of mature oocytes available for cryopreservation relative to AFC compared to FSH alone?

We theorize that supplementation with FSH + rLH will increase the yield of mature MII oocytes among patients with non-hormone sensitive cancer undergoing fertility preservation compared to those with FSH alone. In addition, we anticipate the following trends among patients in the FSH + rLH group compared to those supplemented with FSH alone:

- Higher number of total oocytes retrieved per cycle
- Higher "Follicular Output Rate" (FORT), defined as ratio of pre-ovulatory follicles (16-22mm) on day of trigger divided by AFC [22]
- Higher number of cryopreserved embryos (if patient chooses to freeze embryos rather than oocytes)
- No significant difference in incidence of moderate-severe OHSS

5. Rationale

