7.6 Outcome measures

The primary outcome measure will be the total number of mature (MII) oocytes adjusted by antral follicle count (AFC) available for cryopreservation.

Secondary outcome measures will include the following:

- Total number of oocytes retrieved per cycle
- Ratio of mature (MII) to immature oocytes
- Total number of mature oocytes (MII) retrieved per IVF/ICSI cycle
- Oocyte yield (defined as the number of metaphase II (MII) oocytes retrieved divided by the number of follicles ≥15 mm on ultrasound on the day of trigger)
- "Follicular Output Rate" (FORT) (defined as ratio of pre-ovulatory follicles (16-22mm) on day of trigger × 100/AFC (3-8mm) [22]
- Incidence of moderate to critical OHSS based on the classification criteria by Golan et al [26].
- If the embryos are frozen:
 - o Fertilization rate, which will include two outcomes each defined as follows:
 - Definition 1: number of 2PN zygotes divided by the number of mature oocyte(s) fertilized per IVF/ICSI cycle.
 - Definition 2: number of 2PN zygotes divided by the number of oocytes incubated with at least 10,000 sperm per IVF cycle.
 - Total number of good quality day 5 embryos available for cryopreservation determined by an embryologist using the classification system by Gardner and Schoolcraft, 1999 [25].
- Dose-adjusted evaluation of the safety and tolerability of follitropin alfa + lutropin alfa compared to follitropin alfa as measured by incidence of:
 - o Treatment-emergent adverse events (TEAEs)
 - Treatment-related adverse events (AEs)
 - o Incidence of thromboembolic events

8. Study methods

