8.2 Drug formulation, dosage, and reimbursement

The dosing and drug formulations are adherent to the care provided to our cancer patients seeking fertility preservation in our clinic.

Patients will undergo a random start of ovarian stimulation as per the standard of care in our clinic for all onco-fertility patients given that their treatment is time sensitive. Baseline estrogen, progesterone, LH, FSH, HCG levels are measured and a transvaginal ultrasound is performed and the stage of the cycle is determined. Ovarian stimulation will be performed according to results of the transvaginal ultrasound:

- Early follicular phase: FSH and rLH stimulation or FSH alone will be started as per randomization process. A GnRH antagonist will be given once the dominant follicle measures >1.4 cm.
- Mid to late follicular phase: patients who have a dominant follicle >1.5 cm with an E2 >300 and a progesterone <5 will be triggered with human chorionic gonadotropin (hCG, Ovidrel) 250 mcg subcutaneously. After three days, gonadotropin stimulation is started.
- Luteal phase starts: stimulation with FSH and Luveris or FSH alone, and once the dominant follicle measure >1.4 GnRH antagonist will be given.

Dosing:

- Recombinant luteinizing hormone (Luveris): daily dose of 75 IU subcutaneously.
- Follicular stimulating hormone (Gonal-F):
 - o If AFC < 15, FSH dose is 300 units
 - o If AFC > 15, FSH dose is 200 units
- GnRH antagonist dosing: either cetrorelix 250 mcg subcutaneous or ganirelix 250 mcg subcutaneously.
- Trigger of ovulation: Ovidrel 250 mcg or GnRH agonist (Suprefact 0.5 mg).

FSH dosing is based on a retrospective analysis of data from our centre. A multiple regression analysis found only AFC and AMH to be independently associated with higher number of mature oocytes. AMH is unavailable at the start of the treatment cycle as patients require to start chemotherapy immediately. Accordingly, FSH dosing will be based on AFC. Retrospective review of FSH dosing of our centre showed that when the AFC is less than 15, the majority of patients receive an FSH dose of 300 units to maximize the number of oocytes retrieved. When the AFC is equal to or more than 15, the majority of patients receive an FSH dose of 200 units to minimize the risk of ovarian hyperstimulation. FSH dosing in this trial will correspond to this dosing schedule.

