12.2 Planned analysis

The analysis will be performed on an intention-to-treat principle. Continuous variables will be examined for normality using a normal probability plot. Normally distributed continuous variables will be compared using Welch's t-test. Continuous variables not normally distributed will be compared using Mann-Whitney U test. Categorical data will be reported as counts with percentage, and compared with chi-square test or Fisher's exact test whenever appropriate. Additional sensitivity analysis will be performed taking into account potential confounding factors (i.e. Age, AMH, AFC). Regression analysis with age and FSH dose as factors will also be performed. Statistical analysis will be performed using R statistical software (R Foundation for Statistical Computing).

13. Trial registration

The clinical trial will be registered and available online at www.clinicaltrials.gov once the protocol is approved by the Mount Sinai Hospital Research Ethics Board.

14. Knowledge translation

The lack of consensus on the safety and efficacy of rLH in addition to FSH for ovarian stimulation calls for high quality randomized trials. Once the trial is completed and results are available, knowledge translation is of critical importance and involves the translation of findings to policy and practice [30]. Several procedures will be implemented to share the results of this trial internationally given the increasing number of young patients diagnosed with cancer. The study results will be firstly presented at international fertility conferences. The results will also be published in a high impact fertility journal, such as *Human Reproduction*. Experts in the field will be contacted to ensure they are aware of trial results.

15. Role of principal investigator

[name] is a reproductive endocrinologist at Mount Sinai Fertility as well as a Professor in the Department of Obstetrics and Gynecology at Mount Sinai Hospital. She will be supervising all aspects of the trial.

16. References

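### The 3-8 mm AFC that scales FORT and, on the study question's wording, the primary outcome has no fixed scan under random start, may not be comparable across start phases, and start phase is not used in the analysis

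*Protocol*

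**What the plan says.** AFC enters the outcomes twice. The study question (section 3) asks about a "greater proportion of mature oocytes available for cryopreservation relative to AFC", which makes AFC a denominator. Section 7.6 defines the primary outcome less specifically as the "total number of mature (MII) oocytes adjusted by antral follicle count (AFC) available for cryopreservation", without saying whether that means a ratio, an offset or a covariate. For FORT there is no doubt: 7.6 defines it as the "ratio of pre-ovulatory follicles (16-22mm) on day of trigger × 100/AFC (3-8mm").

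Section 7.5 lists "Ovarian reserve: AMH and AFC (3-8mm) based on the FORT criteria [22"]. This gives the size window for AFC but no scan date and no cycle phase for the count.

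Section 7.1 says that "a random start of the treatment cycle is the usual approach in our clinic, with no prior priming". Sections 7.1 and 8.2 describe one transvaginal scan before stimulation, from which the cycle stage is determined. In 8.2, "Ovarian stimulation will be performed according to results of the transvaginal ultrasound". Early follicular and luteal starters go on to gonadotropins. A further group, "Mid to late follicular phase: patients who have a dominant follicle >1.5 cm with an E2 >300 and a progesterone <5", is given hCG first and starts gonadotropins after three days.

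Randomisation (8.1) is stratified by age only. Section 12.2 says "Additional sensitivity analysis will be performed taking into account potential confounding factors (i.e. Age, AMH, AFC") and adds a regression on age and FSH dose. Neither section mentions start phase. Section 7.5 lists the type of cycle start among the treatment-cycle characteristics, with two levels: follicular and luteal.

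**The concern.** A 3-8 mm count can stand for the recruitable cohort when it is taken just before stimulation with no follicle yet selected. A mid to late follicular starter is in a different position at the described scan. At least one follicle exceeds 15 mm, every follicle above 8 mm is outside the window by definition, and the patient receives an hCG trigger and waits three days before stimulation. If the outcome AFC comes from that scan, the same variable may mean different things in different start-phase groups while scaling FORT, and possibly the primary outcome, for everyone.

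What is at stake is precision and interpretability. Phase-dependent error in a denominator adds variance to a ratio. The plan names no adjustment for phase. The two-level start field merges early with mid to late follicular starts, which is the distinction that matters, so a later analysis could not make the adjustment from the listed field alone.

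**Working it through.** **The plan's own figure.** Section 12.1 uses a control mean of 8, SD 4, a difference of 10 − 8 = 2, two-sided alpha 5% and power 80%:

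(4² + 4²)(1.96 + 0.84)² / 2² = 32 × 7.84 / 4 = 62.72, so 63 per group and 126 in total. 126 / 0.9 = 140.

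The stated 126 and 140 reproduce. They apply to the raw oocyte count, not to a count scaled by AFC. The simulations below take 63 per arm and the 10 versus 8 contrast (a factor of 1.25) from here.

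**Inputs that the documents do not give.** These are the share *p* of patients who start mid to late follicular, and the fraction *f* of the responding cohort that lies outside 3-8 mm at the AFC scan. Both are assumptions and are shown over ranges.

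**Simulation 1.**
- Responding cohort C: negative binomial, mean 15, dispersion 6, minimum 4.
- MII: negative binomial, mean 8·C/15 (times 1.25 with rLH), dispersion 9. The raw SD is about 5.5, above the planned 4, so powers should be compared with each other and not with 80%.
- AFC = C, except Binomial(C, 1 − f) in mid to late follicular starters.

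With p = 35%, mean control MII/AFC in those starters is 0.53 at f = 0, 0.68 at f = 0.2 and 0.96 at f = 0.4. Power:

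| Analysis | f = 0.2 | f = 0.4 |
|---|---|---|
| Welch test on MII/AFC | 0.63 | 0.45 |
| MII on arm + AFC | 0.68 | 0.60 |
| MII on arm + AFC + three-level start phase | 0.69 | 0.63 |

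With no undercount, the Welch test on the ratio has power of about 0.68. With 3,000 replicates the Monte Carlo standard error is √(0.65 × 0.35 / 3000) ≈ 0.009, so a gap of 0.01 is noise.

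A further run added AFC-by-phase terms, with 25% luteal starts assumed. Power without phase versus with phase and interaction was 0.666 v 0.652 at f = 0.1, 0.673 v 0.673 at f = 0.2, and 0.618 v 0.655 at f = 0.4. The interaction does not earn its place.

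**Simulation 2, a different model.** True AFC has mean about 15, MII is proportional to AFC, the true effect is 25%, 20-33% of patients are mid to late starters, and their AFC carries random error on top of the undercount. All figures are for MII/AFC.

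| Undercount | Welch test | Adjusted for mid to late start |
|---|---|---|
| none | about 62% | – |
| 10% | 59-61% | 59-61% |
| 30% | 52-53% | 54-56% |
| 50% | 37-40% | 46-49% |

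Type I error was 4.6-5.3% without adjustment and stayed near 5% with it.

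**Size of a chance imbalance.** With p = 35% and 63 per arm, the SD of the between-arm difference in start share is √(2 × 0.35 × 0.65 / 63) = 0.085. Multiplied by the phase difference in control ratio, this is 0.085 × (0.68 − 0.53) = 0.013 at f = 0.2 and 0.085 × (0.96 − 0.53) = 0.037 at f = 0.4. The assumed effect on the ratio is 0.25 × (0.65 × 0.53 + 0.35 × 0.68) = 0.146 and 0.25 × (0.65 × 0.53 + 0.35 × 0.96) = 0.170. One SD of imbalance is therefore about 9% to 21% of the effect.

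**Cost of adjusting.** If AFC does not depend on phase, two extra covariates raise the variance of the arm effect by roughly 2/(126 − 5) ≈ 1.7%.

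**The case against.** Four objections deserve weight.

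First, no section says which scan supplies the outcome AFC, and none rules out a recount when stimulation starts after hCG. A reader might infer that AFC in mid to late starters definitely predates stimulation by at least three days. That is the natural reading of a protocol that describes one pre-stimulation scan, but it is not stated. The firm defect is that the scan is not fixed.

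Second, a reader might infer that MII/AFC and FORT are inflated in these patients. For example, 6 follicles inside the window, 4 outside it and 10 pre-ovulatory follicles at trigger give FORT = 100 × 10/6 = 167%. This requires follicles above 8 mm to survive the hCG trigger and the wait and then join the stimulated cohort. The documents do not say that they do. If they do not, leaving them out of the denominator inflates nothing. Both simulations rest on the same premise.

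Third, most of the power recovered at f = 0.4 comes from using AFC as a covariate instead of a divisor (0.45 to 0.60), and phase adds 0.03. Section 7.6 would already permit the covariate form. This stands, and it is why the remedy begins with the form of the model.

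Fourth, an extra covariate could be left to an SAP that is not shown. That is true of the covariate, but not of the data: an SAP cannot recover the early versus mid to late distinction from a two-level field. Nor does it excuse an outcome component with no fixed time point in an open-label trial.

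**Conclusion.** The point holds as a matter of measurement definition and precision. The 3-8 mm AFC is FORT's denominator and, on the wording of section 3, that of the primary outcome. It is taken under random start without a rule for which scan counts. It may not be comparable between mid to late follicular starters and the rest, and the plan neither stratifies nor adjusts for start phase nor records it finely enough to do so.

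The size cannot be fixed from the documents, because neither the share of mid to late starts nor the undercount is given. Under the stated assumptions the loss is small at a 10-20% undercount and substantial for the ratio only from about 30-40%. If the primary outcome is read as a covariate-adjusted count, the exposure there is smaller; FORT is exposed on either reading.

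A reader might infer a biased comparison, or a chance imbalance passing for a drug effect. The documents do not support that. Randomisation balances start phase in expectation, and type I error stayed near 5%, so chance imbalance is already covered by the test's error rate. The case for changing the plan is that a baseline factor the clinic already determines in every patient can be used at almost no cost.

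**What to change.** - **12.2:** make the primary comparison a model of the MII count on arm, with AFC and start phase as main-effect covariates, in place of an unadjusted test of MII/AFC. No AFC-by-phase interaction is needed.
- **7.6:** compare FORT adjusted for start phase.
- **7.5:** record start phase in three categories (early follicular, mid to late follicular, luteal). State one rule, the same for all patients, for which already-performed scan supplies AFC relative to the first gonadotropin dose.

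The cost is wording in three sections, one expanded data field and two model degrees of freedom. If AFC turns out not to depend on phase, the variance of the arm effect rises by about 1-2%. No extra scan is needed and treatment is unchanged.
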